3 STUDY DESIGN

3.1 Study Design

- NIH Behavioral Intervention Stage 1 randomized pilot trial to examine the acceptability and preliminary effects of the STEP-UP program on pain interference among older adults with chronic pain compared to a control group.
- Participants will be allocated into the two study arms in a 1:1 ratio by block randomization with mixed block sizes.

3.2 Study flow

4

5 SELECTION AND ENROLLMENT OF PARTICIPANTS

5.1 Inclusion Criteria

Participants will be eligible if they:

- Are 50+ years of age
- Report high-impact chronic musculoskeletal pain (defined as pain in muscles or joints for ≥ 3 months “most days” or “every day” on a scale of never, some days, most days, or every day) AND their pain limited life or work activities over the past 3 months “most days” or “every day”
- Have a cell or landline phone
- Able to converse comfortably in English
- Have not participated in another chronic pain self-management intervention in the last 5 years.
- Participants must be willing to meet by telephone with a Community Health Worker and listen to audio recordings (podcasts) to learn ways to manage pain and commit to the duration of the program. However, the study is voluntary, and participants may leave the study at any time.

5.2 Exclusion Criteria

- Hospitalization in the last month
- Planned major surgery in the next three months that would interfere with program participation (e.g., knee or hip replacement)
- Current or previous participation in either the STEPS or RESET interventions
- Severe cognitive impairment or other severe physical or psychiatric disorder judged by the study team to pose a significant barrier to participation

5.3 Recruitment

Recruitment for this study will take place through the Western Wayne Family Health Center (WWFHC). Several options for recruitment may be used: 1) By identifying potential participants age 50+ with specific diagnostic codes in the electronic medical record (EMR) system and sending them a letter and/or text message/portal message (sent out directly by WWFHC to patients; this process will be done in waves by zip code so that screening and enrollment can be done on a steady, “rolling” basis); 2) by making flyers available in clinic areas (either tables staffed by the UM study team or leaving flyers out for patients to pick up on their own - in the case of UM staffed tables, we will ensure that any screening that happens would take place by trained and IRB-approved UM study staff in a private location off the main clinic); and 3) direct referrals by WWFHC providers. In the case of direct referrals by WWFHC providers, the providers would give the patient a study flyer and/or the UM study team’s contact information so the patient can reach out to the UM study team for more information and next steps. The UM study team **will not** receive any patient information directly from WWFHC. Potentially eligible patients will be informed about the study team by WWFHC and directed to contact the UM study team if they are interested in learning more.

Three versions of the study flyers will be available; a simple version with the UM study hotline number and UM study email (used for tabling and recruitment events located at WWFHC and in the community; some WWHFC patients/providers may prefer the simpler version), a version with tabs so interested individuals can take the UM study team's contact information to contact later (for posting at WWFHC and in the community), and a QR code version where interested individuals can use their smartphone camera to scan the code and complete a brief interest form via UM Qualtrics (used for tabling and recruitment events located at WWFHC and in the community). The UM study team will receive automated emails when individuals leave voicemails on the study hotline number and when someone completes the UM Qualtrics interest form. The UM study team will add interested individuals to the REDCap database and reach out to them within one week of receiving their interest form and/or voicemail to follow up accordingly.

5.4 Informed Consent & Enrollment

During recruitment contacts each patient will hear a brief description of the study before being asked if they wish to be screened for eligibility. In addition to meeting eligibility criteria, participants must be willing to meet by phone with a community health worker and listen to audio recordings (podcasts) to learn ways to manage pain and commit to the duration of the program. Interested individuals will be screened by trained and IRB-approved UM study staff on site or by telephone to further assess eligibility and invite to participate, if appropriate.

If a patient expresses interest in participating in the study by contacting the UM study team or at a tabling event, UM study staff will follow up with the patient by telephone (UM Zoom Phone) to see if the participant is interested and, if so, go through the eligibility screener with the patient using the study's UM REDCap database. After this they will complete the verbal consent process over the telephone. This can be completed directly after the screening process, or the patient can schedule it for another time.

In some cases, if there is time and private space available at the WWFHC clinic when UM study staff tabling and handing out flyers, UM study staff may go through the eligibility screener questions with the participant in-person at the clinic then schedule a telephone follow up to complete verbal consent process and next steps. If in-person, UM study staff would record the patient's responses to the eligibility questions on a paper version and enter the responses into REDCap directly after the recruitment event. Paper versions of the eligibility questions will be kept securely in the UM study team's locked office at the University of Michigan School of Public Health. If the participant is eligible, the UM study staff will confirm a day and time to follow up with the participant and complete the verbal consent process over the telephone.

For both, telephone and in-person screening, participant responses to the eligibility questions will be kept securely in the REDCap database.

Participants who are eligible will be offered more details about the study. They will be told that those agreeing to participate in the research will be randomly assigned to one of two groups (with an equal chance of being in either), after completing informed consent and a baseline telephone survey.

The intervention and control conditions will be described as follows. Individuals in the intervention group will meet with a community health worker for a 1-1.5 hour orientation session (typically in person but may be virtual in special cases described in Section 6.2) to get oriented to the program, receive a hard-copy workbook, and engage in a values-clarification and goal-setting exercise. Participants will then be asked to listen to one podcast episode per week for five weeks, each presenting a new pain self-management skill. Podcasts will be made available by both website and an IVR system. Each week, participants will receive a reminder text, voicemail, and/or brief telephone call from the CHW encouraging them to listen to that week's podcast episode, complete corresponding tasks as described in the workbook, and continue to work on their goal. After completing the follow-up telephone survey at 2 months from baseline (see below), individuals in the control group will be invited to take part in the intervention.

Participants in both groups will be asked to complete two data collection telephone interviews (at baseline and 8 weeks from baseline), each of approximately 45 minutes in length.

Informed consent procedures: If an eligible individual expresses interest in participating, they will be asked to verbally consent over the phone, either right away or on a subsequent call, according to participant preference and whether the participant completes the eligibility screener in-person or over the phone as mentioned earlier in Section 5.4. Participants will have the option to have a copy of the consent document mailed or emailed to them to review beforehand, or they can choose to complete the verbal consent first and have a copy of the consent document mailed or emailed to them afterward. The consent document will be mailed in a packet that also contains survey scale options for the initial, baseline survey. These are the response options for each of the survey items so the participant can more easily follow along on the telephone.

During the verbal consent process, the interviewer will read the informed consent document aloud, stopping to ask questions after each section. The verbal consent is documented in three ways. 1) With the participant's permission, we will audiorecord the verbal consent interaction (using UM Zoom or UM Zoom Phone) and securely store the audiofiles in access-restricted UM Dropbox folders. 2) We write their full name, the date, and the interviewer's initials to document that verbal consent was obtained in REDCap. 3) We will also indicate in REDCap that verbal consent was provided and document the date.

For participants who choose to have the consent document mailed to them first, research staff will call potential participants approximately one week after mailing the consent document to go through the verbal consent process over the phone and answer any questions. If the participant preferred an emailed copy of the consent document, research staff may call sooner based on the participants preferences.

Upon completing verbal consent, the participants will be enrolled in the study and will be scheduled for a baseline interview.

5.5 Screen Failures

Individuals who sign the consent document and who subsequently are deemed ineligible or inappropriate for participation (e.g., unable to participate meaningfully in study activities, discovery that diagnoses are not consistent with study criteria, etc.) will *not be enrolled*, but instead classified as "screen failures."

5.6 Strategies for Recruitment and Retention

Recruitment: We expect that the strategies outlined in Section 5.3 will yield enough participants for this pilot study, and we expect that most participants will be WWFHC patients. However, if needed, we will recruit from outside of the clinic, by working with the network of senior centers and senior housing facilities in the Detroit area with which we have developed relationships over several years, using flyers, information sessions, and word of mouth to advertise this study.

Information sessions will be done by trained UM study staff. These would be done at WWFHC clinics or at a senior center/senior housing center. During the information sessions, UM staff provide an overview of the study and answer questions about study participation. Individuals who attend the information session will be invited to provide their contact information to the study team for follow up, if they are interested in participating. In some cases, if time and space allows, the study team may complete the study eligibility screener in-person with the participant and schedule them for a verbal consent over the telephone, as described in Section 5.4.

Retention: We will follow detailed protocols that we have successfully used in past studies with older adults from vulnerable populations to try to retain participants once enrolled, including making a specific number of contact attempts at different times, with the goal of maximizing retention without being bothersome to participants or coercive. Specifically, these are the guidelines we will follow:

- We will call each participant 10 times without answer or response before marking them as Lost to Follow-up (Unable to Contact).
- If we call someone and the number is disconnected, we will arrange for a call-back one week later. If we call then and it is still disconnected we will arrange for a call-back two weeks later, and, if we have their address, mail them an “Unable to Contact” letter. If we call then and it is still disconnected, we will arrange for a call-back one month later. If it still disconnected at that point, we will mark the participant as Lost to Follow-up (Unable to Contact).
- We will reschedule a participant's baseline survey 5 times. We will reschedule the follow-up as many times as it takes to get the participant to complete it, until a one-month window from when the ideal follow-up date has passed (the ideal follow-up date is two months from baseline).
- We will attempt to contact a person for their follow-up survey 5 times; then send an Unable to Contact letter. If we do not hear from them, we will contact them a total of 5 more times.
- We will reschedule attendance at the orientation session (intervention participants only) a maximum of 3 times.
- All contact attempts will be documented in REDCap.

We will offer incentives for each data collection point. All incentives are provided in the form of gift cards from the Human Subjects Incentive Program at the University of Michigan. Participants will receive a \$20 gift card incentive for the first data collection point and a \$30 gift

card incentive for the second data collection point. Participants will also be given an inexpensive pedometer to count their steps during the program, if they choose to, and as an additional incentive. The study team will not ask participants to report their step counts as part of the study data.

In the STEP-UP intervention group, we will track session adherence. The CHW will be provided with guidelines for contact frequency. If participants do not respond back to the CHW, the study team will reach out to see if there are any issues that can be solved to increase engagement.

6 STUDY INTERVENTIONS

Participants will be randomized to one of two study arms in a 1:1 ratio: Arm 1 will receive the STEP-UP intervention and Arm 2 will be in the control group and will be waitlisted to be invited to receive the intervention.

6.1 STEP-UP Intervention Overview

STEP-UP will feature a podcast series teaching core pain self-management skills. Podcasts will be accompanied by regularly scheduled telephone sessions with a community health worker, who will guide participants in a modified Patient Priorities of Care (PPC) approach (originally developed for older adults with multiple chronic conditions) to identify their most important values and health outcome goals, and healthcare preferences. This information will inform self-management goals and will be shared with providers to promote patient-centered pain care.

6.2 STEP-UP Intervention Process

Orientation session: Intervention participants will meet in person with a CHW for a one-time study orientation (about 1-1.5 hours for most participants) to get oriented to the program, receive a hard-copy workbook, and respond to a brief social needs screener (PRAPARE), allowing the CHW to make referrals to any needed resources. The orientation session will typically be in person, but it may be completed virtually, via UM Zoom link, in special cases such as transportation barriers, scheduling challenges, patient mobility issues, and/or for public health reasons like COVID-19. The UM team will also try to provide transportation for participants to get from their home to the WWFHC clinic if that is a barrier to attending the orientation in-person (like Green Cab or Uber/Lyft). The orientation will be completed in private location where the CHW and participant can speak comfortably. For the social needs screener, the CHW will read the PRAPARE questions out loud and record the participant's answers to the questions in UM REDCap database. The participant can choose to decline answering any of the PRAPARE questions they prefer not to answer. Based on the participant's responses, the CHW will provide community-based resource referrals (such as organizations serving seniors, senior centers, food-related resources, local health department information, etc.). Contact information for referrals will be given to the participant at the orientation so they can follow up if they choose to.

Participants will also engage in a values-clarification exercise (“What Matters Most”, in the domains of Connecting, Enjoying Life, Managing Health, Functioning) and goal-setting process, adapted from the Patient Priorities Care model. Participants will set meaningful activity goals that reflect their values. This process will include completing a “My Pain Priorities” summary sheet that can be shared with their provider, which includes information about care that they perceive as helpful or burdensome. The CHW will also complete a fillable form for each participant that states that they are taking part in the STEP-UP study and will include the information from the My Pain Priorities summary sheet. The CHW or study staff will fax this form to the WWFHC secure fax line for patient information and it will be uploaded by WWFHC into the patient’s Electronic Health Record (EHR). This is a way for the CHW to put information into the EHR without having to have their own access to the EHR system. By adding the participant’s My Pain Priorities summary sheet to their EHR, the participant’s healthcare providers can see what the participant’s goals and values are for a patient-centered approach to pain management. This may better facilitate conversations between the patient and the provider related to values and priorities. At this orientation, participants will also learn how to access the audio recordings (podcasts) and they will choose a time for weekly telephone sessions with the CHW.

Subsequent sessions: Participants will be asked to listen to one podcast episode per week, each presenting a new self-management skill along with motivational elements to try out the new skill. Podcast audiofiles will be made available on a website or “dial in.” Each week, participants will receive a reminder text, voicemail, or phone call from the CHW (based on their preferences) encouraging them to listen to that week’s podcast episode, complete tasks as described in the workbook, and continue to work on their values-informed behavioral goal.

During the final week, participants will have a 30-minute wrap-up session with the CHW. This final session can be done in-person or by telephone, depending on the participant’s preferences. At this final session, they will reflect on progress made, establish a goal to work on going forward, and receive encouragement to discuss their “My Pain Priorities” summary sheet with their provider if they haven’t already. See the table below for more details about the six weekly sessions.

STEP-UP Intervention Content

Week	Format/ CHW contact	Main topics
Week 1 Orientation	1-1.5 hr, in person with CHW (Zoom as back up option)	
 - How STEP-UP program will work - Provide workbook, pedometer, and other materials (e.g., PPC) - Podcasts: explain and practice accessing - Chronic Pain 101: How body and brain process pain signals, holistic approach to managing pain and maintain quality of life - Introduce Patient Priorities of Care approach (via video with discussion): Values identification and SMART goal - Administer SDOH screener (PRAPARE) and provide resources
Week 2 Staying Active	CHW 30 min phone session	
 - How physical activity helps with pain and fatigue - Strategies for incorporating physical activity into daily routine - Explore opportunities for physical activity and resources - Problem-solve barriers and challenges - Goal check-in
Week 3: Relaxing and Reducing Stress	CHW 15 min phone session	
 - Explore how stress and pain are linked - Introduce relaxation techniques (deep breathing, guided imagery, PMR) - Goal check-in
Week 4: Partnering with Your Provider	CHW 30 min phone session	
 - Review Patient Priorities Care approach; sharing worksheet with provider - How to get the most out of healthcare visits and planning for visits
Week 5: Doing What You Love	CHW 15 min phone session	
 - Importance of making time for well-being, self-growth, and fun - Identify ways to incorporate pleasant activities into daily life
Week 6: Moving Forward	30-min CHW phone or in-person session	
 - Review of sessions and strategies presented - Celebrate successes and progress - Establishing long-term goals and plan for “relapse” - Identify helpful resources moving forward

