6.10 Withdrawal from the Study

If participants withdraw or decline to finish the intervention, every effort should be made to gather primary outcome data (pain interference) as well as a query about adverse events.

- The goal is to collect the information as close to the designated follow-up assessment as possible (8 weeks). Participants need to complete the assessment within one month of the follow-up date in order to be counted as non-missing.
- For intervention group participants wishing to discontinue participation in the intervention, the study team member will ask to call them during the scheduled follow-up window.
- Participants who state that they wish to withdraw completely from the study will not be contacted further.

The reason for participant discontinuation or withdrawal from the study will be recorded in REDCap. Participants who sign the informed consent form and are randomized to the intervention but do not begin it will not be replaced, due to the short overall study period. Participants who sign the informed consent form, and are randomized and receive the study intervention, and subsequently withdraw, or are discontinued from the study, will not be replaced.

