7 STUDY PROCEDURES

7.1 Schedule of Activities

Activity	Weeks									
	Pre	0	1	2	3	4	5	6	7	8
Eligibility Screening	X									
Consent Process	X									
Randomization	X									
Demographics		X								
Chronic conditions and overall health		X								
Pain Interference (PROMIS-43 6-item scale)		X								X
PROMIS-29 +2 ^{14,15} (except Pain Interference subscale)		X								X
Pain Intensity (Numerical Rating Scale)		X								X
Pain Self-Efficacy Questionnaire		X								X
Pain Medication Use		X								X
Communication with Provider		X								X
Chronic Pain Acceptance		X								X
Physical Activity		X								X
Fear of Movement		X								X
Patient Activation Measure		X								X
Survey of Pain Attitudes (SOPA) - Control subscale		X								X
Pain Catastrophizing Scale		X								X
Life Control Scale		X								X
PROMIS Meaning and Purpose (4-item)		X								X
Global impression of change in pain, functioning, quality of life, and use of pain medication										X
STEP-UP Program Evaluation Questions (intervention group only; both close- and open-ended)										X

STEP-UP: CHW sessions (intervention group only)				X	X	X	X	X	X		
---	--	--	--	---	---	---	---	---	---	--	--

Notes:

*Shaded rows represent measures on the telephone data collection surveys (at baseline and/or 8 weeks).

**Primary and secondary outcomes are bolded.

***Allowable assessment windows: Participants need to complete the assessment within one month of the follow-up due date to be counted as non-missing.

****If participant does not start intervention within one month of baseline assessment, they will be withdrawn from the study by the study team. If a participant drops out of the intervention, they will be invited to complete the surveys if they want to (intent to treat) or they can withdraw from the study.

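### Eligibility covers only telephone sessions and podcasts, and no specific check before randomization asks whether a person can attend the in-person or Zoom orientation

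*Combined protocol and SAP*

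**What the plan says.** All references are to the combined protocol and SAP.

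**Eligibility.** Section 5.1 sets one equipment requirement, "Have a cell or landline phone", and one on mode of contact: "Participants must be willing to meet by telephone with a Community Health Worker and listen to audio recordings (podcasts". The same sentence goes on to ask for commitment to the whole program, and section 5.4 repeats it. Neither criterion mentions travel to the clinic or use of Zoom.

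**Entry to the program.** The content table in section 6.2 gives the first session as "1-1.5 hr, in person with CHW (Zoom as back up option". The text of 6.2 adds that "it may be completed virtually, via UM Zoom link, in special cases such as transportation barriers, scheduling challenges, patient mobility issues". The wrap-up session may be by telephone; for the orientation no such option is stated.

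**Safeguards before randomization.** Section 5.4 has staff describe the orientation to candidates as "typically in person but may be virtual in special cases described in Section 6.2". Section 5.2 excludes "Severe cognitive impairment or other severe physical or psychiatric disorder judged by the study team to pose a significant barrier to participation". Section 5.5 classes people who consent but prove unable to take a meaningful part as screen failures.

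**After randomization.** Section 7.2 places randomization after the baseline telephone survey, and orientation follows it. Section 5.6 caps rescheduling of the orientation at three, for intervention participants only. A note to section 7.1 states: "If participant does not start intervention within one month of baseline assessment, they will be withdrawn from the study by the study team". Section 6.10 says that people who are "randomized to the intervention but do not begin it will not be replaced". Controls need only the two telephone surveys before the 8-week outcome (section 6.3).

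**The concern.** The criterion that a candidate must satisfy does not match the session that starts the program. Someone who cannot reach the clinic within the time allowed and cannot use a Zoom link can meet every stated criterion and be randomized. If allocated to the intervention, that person may be unable to start, and the note to 7.1 then takes them out of the study. A control with the same barrier is surveyed at 8 weeks as planned.

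Two things are at stake. Removal after randomization in one arm can make the arms non-comparable on the primary outcome, pain interference. And non-starts caused by access would be mixed with non-starts caused by lack of interest, which blurs the engagement result that this pilot is meant to deliver.

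**Working it through.** The plan gives no power, dropout or non-start figure to reproduce, so the check is first textual and then illustrative.

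**Text, in order of events.**
1. Screening and consent: the criteria concern telephone and audio only (5.1, 5.4). Orientation is disclosed, but ability to attend is not asked.
2. Baseline survey by telephone, then randomization (7.2).
3. Intervention arm: orientation in person or by Zoom (6.2), at most three reschedulings (5.6), withdrawal from the study if not started within one month of baseline (7.1 note), no replacement (6.10).
4. Control arm: no start condition before the 8-week survey (6.3). The 7.1 note therefore has nothing to act on in controls during that period.
5. Handling of those who stop: 6.10 seeks the primary outcome from people who withdraw or do not finish, and 11.2.3 includes everyone randomized to the intervention. The 7.1 note itself invites people who drop out of the intervention to complete the surveys, but says nothing similar for non-starters. The plan does not settle whether a withdrawn non-starter is surveyed and analyzed.

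**Illustration.** From the plan: 40 participants at 1:1, so 20 per arm; reference SD of the T-score 10 (11.2.2). Assumed: k of 20 intervention participants cannot start (q = k/20); a true benefit of 3 points for those who start and none for those who do not; and affected people would score D points worse than the rest without the program.

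- If non-starters are kept: effect = 3 × (20 − k)/20.
- If non-starters are removed: SE of the difference = 10 × √(1/(20 − k) + 1/20).
- If non-starters are removed: bias in the unadjusted difference, relative to the effect among those able to start, = q × D. The control mean still carries the term q × D; the intervention mean does not.

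| k | q | Effect if kept | SE if removed | Bias, D = 5 | Bias, D = 10 |
|---|---|---|---|---|---|
| 0 | 0% | 3.00 | 3.16 | 0 | 0 |
| 1 | 5% | 2.85 | 3.20 | 0.25 | 0.5 |
| 2 | 10% | 2.70 | 3.25 | 0.5 | 1.0 |
| 4 | 20% | 2.40 | 3.35 | 1.0 | 2.0 |
| 5 | 25% | 2.25 | 3.42 | 1.25 | 2.5 |

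The SE rises by about 1%, 3% and 6% for k = 1, 2 and 4, which is immaterial here. The bias reaches the 2.5 points that section 2 calls clinically significant only in the extreme corner, q = 25% with D = 10. The baseline covariate in 11.2.2 would remove part of it. If affected people would score better than the rest, the sign reverses. If access is confirmed before randomization, or non-starters are surveyed and analyzed as randomized, the bias from this cause is zero.

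**The case against.** The case against is substantial.

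- **Disclosure and discretion already exist.** Candidates hear about the orientation before consenting and must commit to the program; 5.2 and 5.5 let the team exclude people who could not take part. A reader might infer that screening looks at telephone contact alone. The documents do not support that. What stands is narrower: these routes rely on self-exclusion or general discretion, and none asks whether the person can attend in one of the two modes.
- **The affected group is small.** It needs no usable Zoom access, a barrier that neither a ride (which the team will try to provide, 6.2) nor three reschedulings solves, and commitment despite disclosure. A reader might infer that such people will certainly be randomized and lost. The documents do not show this; the number could be zero. Nor do landline eligibility and dial-in podcasts show that the plan expects participants without internet; they only accommodate them.
- **The loss comes from the withdrawal note, not from section 6.2.** This is correct. With 7.1 reconciled with 6.10 and 11.2.3, what remains is ordinary intention-to-treat dilution, which is not bias. The fall below 2.5 in the table also depends on assuming a true benefit of exactly 3; 11.2.2 itself uses 3 as the minimally important difference.
- **Failure to start is a feasibility result.** Section 2 makes engagement an endpoint partly because barriers are expected, and screening out people with barriers would raise measured engagement. This stands as a cost of the fix. The answer is to count them, which measures the barrier in all candidates, not only in those allocated to the intervention.

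**Conclusion.** The mismatch between the criterion in 5.1 and 5.4 and the entry modes in 6.2 is real, and no specific check closes it before randomization. Its size cannot be derived from the documents: zero to a few of about 20 intervention participants is an assumption. The bias risk comes from removal in one arm under the 7.1 note. Under the assumed range of 1 to 4 removed, it is 0.25 to 1.0 T-score points for D = 5 and 0.5 to 2.0 for D = 10, before baseline adjustment. The asymmetry concerns this mechanism only; controls can be lost for other reasons. Precision is barely affected, and section 11.1 says that the pilot is not powered for significance in any case. This is a worthwhile, inexpensive correction and not a threat to the trial as a whole.

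**What to change.** 1. Add the orientation to the willingness criterion in 5.1 and 5.4, so that it agrees with the modes in 6.2.
2. Before randomization, ask every candidate whether they can attend by one of those modes, with a ride if needed, within the period in the 7.1 note. Randomize only those who can.
3. Report those who cannot as a feasibility result, using the screen-failure route in 5.5. As worded, that route begins at consent, so if the question is asked at the eligibility screener, count people stopped there too.
4. Reconcile the 7.1 note with 6.10 and 11.2.3, so that anyone who still does not start is followed up at 8 weeks and analyzed as randomized.

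How the orientation is delivered remains the sponsor's decision.

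The cost is one screening question and some protocol wording. The sample becomes slightly narrower, and measured engagement will describe people able to attend orientation. It should therefore always be reported beside the count of those unable to attend.
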